# 7.3 Visit during the randomization phase

#### 1) Within the first cycle after administration:

Blood routine examination is performed once a week.

The vital signs, urine routine, stool routine, liver and kidney function examination, electrolyte test, serum Tg and TgAb levels, thyroid function test and electrocardiogram examination should be carried out once every two weeks. In case of precordial pain, palpitation and other symptoms,

myocardial enzyme spectrum should be detected immediately, and cardiac color Doppler ultrasound should be performed

Physical examination, coagulation function test, ECOG PS score, imaging examination and life quality score are performed at the end of the first week.

Blood pressure monitoring: subjects should be monitored at least three times per week. During blood pressure measurement, smoking and coffee consumption should be avoided for at least 30 minutes before measurement, and at least 10 minutes of quiet rest should be taken. During the measurement, the elbow should be put at the same level as the heart in a sitting position.

#### 2) During the second cycle after administration

Vital signs, blood routine, serum Tg and TgAb levels and thyroid function are detected every 2 weeks.

At the end of the second cycle, imaging examination and life quality score are performed. Physical examination, coagulation function test, ECOG PS score, urine routine test, stool routine test, liver and kidney function test, electrolyte test, serum Tg and TgAb level, thyroid function test and ECG examination are conducted. If the symptoms such as precordial pain and palpitation are found, myocardial enzyme spectrum should be detected immediately, and cardiac color Doppler ultrasound should be performed.

Blood pressure monitoring: the same as the first cycle.

#### 3) At the end of the third week after the start of administration and after

Vital signs, physical examination (including skin toxicity, nausea, fatigue, tooth function such as looseness, tooth drop, etc.), ECOG PS score, life quality score, blood routine, urine routine, stool routine, liver and kidney function test, electrolyte test, blood coagulation function test and electrocardiogram examination are performed weekly, in case of precordial pain, palpitation and other symptoms, the myocardial enzyme spectrum should be detected immediately, and cardiac color Doppler ultrasound should be performed (subjects can increase the frequency of selfexamination of vital signs according to their own situation and fill in the relevant abnormal conditions in the research diary. The above examination is changed to once every 2 cycles after 6 cycles of medication.

The efficacy of tumor is evaluated every 2 cycles (imaging examination: CT/MRI/B ultrasound), serum Tg and TgAb levels are detected, and thyroid function is examined.

Blood pressure monitoring: the subjects should self-monitor the blood pressure at least once a week, once abnormal, they need to monitor to the normal level every day, and record in the patient's diary card. During the visit, the researcher measures the blood pressure, and the measurement method is the same as that in the first cycle.

4) The concomitant medication and AE should be observed and recorded at any time from the beginning of administration to 30 days after the end of administration.

# 7.4 Visit during the extension phase

Subjects judged as progressive disease by investigator can be unblinded. If the subjects unblinded, the subjects who is placebo group can decide whether to enter the apatinib group. The subjects in apatinib group begin to receive apatinib treatment until the researchers determined that it is not suitable to continue treatment (including but not limited to progressive disease or intolerance). However, for the subjects who have taken apatinib before after blinding, on the premise of safety and possible effectiveness, they can enter the extension phase, continue to be treated with open-label apatinib, if the subjects themselves are willing and the investigator think it is feasible.

The subjects enter the extension phase visit:

Vital signs, physical examination (including skin toxicity, nausea, fatigue, tooth function such as looseness and tooth loss) and ECOG PS score, life quality score, blood routine, urine routine, stool routine, liver and kidney function test, electrolyte test, blood coagulation function test and electrocardiogram examination are performed every 2 cycles. In case of precordial pain, palpitation and other symptoms, the myocardial enzyme spectrum should be detected immediately, and cardiac color Doppler ultrasound should be performed (subjects can increase the frequency of selfexamination of vital signs according to their own situation and fill in the relevant abnormal conditions in the research diary). Tumor efficacy should be evaluated every 2 cycles (imaging examination: CT/MRI/B-ultrasound), and the serum Tg and TgAb levels, and thyroid function examination are monitored and conducted every 2 cycles.

Blood pressure is monitored weekly and measured by the researcher during the visit.

# 7.5 Visit during follow-up

Subjects with early withdrawal, intolerable AEs, progressive disease in the randomization phase or progressive disease in the extension phase can enter the survival follow-up period.

- If the subjects have been evaluated within 4 weeks before the survival follow-up period, the survival follow-up and imaging efficacy evaluation should be conducted once every 2 months until imaging progression or other anti-tumor treatment is started.
- If the subjects have not been evaluated within 4 weeks before the survival follow-up period, a follow-up and evaluation of therapeutic efficacy (imaging examination, detection of serum Tg and TgAb levels, and thyroid function test (including FT3, FT4, TSH, RT3 [RT3 can be selected as needed]) and then the survival follow-up and imaging efficacy are conducted once every 2 months until imaging progression or other anti-tumor treatment is started.

During the follow-up period, the time of death or loss of follow-up and other anti-tumor treatment is recorded.

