# 2.2 Secondary Objectives

- To assess the overall survival (OS) in subjects treated with apatinib, compared with placebo.
- To assess the objective response rate (ORR) in subjects treated with apatinib, compared with placebo.
- To assess the disease control rate (DCR) in subjects treated with apatinib, compared with placebo.
- To assess the duration of response (DOR) in subjects treated with apatinib, compared with placebo.
- To assess the time to response (TTR) in subjects treated with apatinib, compared with placebo.
- To assess the safety and tolerability of apatinib, compared with placebo.

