# 3 Study Design and Methodology

# 3.1 Overall Study design

This is a multicenter, randomized, double-blind, placebo-controlled clinical trial to evaluate the efficacy and safety of apatinib in the treatment of locally advanced/metastatic radioiodine refractory differentiated thyroid cancer (RAIR-DTC).

The eligible subjects will be randomly assigned to either the treatment group or control group in a 1:1 ratio. Apatinib or placebo will be given 500 mg orally once daily for 28 days. Apatinib treatment will be discontinued at the time of disease progression, intolerable toxicity, withdrawal of consent, or due to investigator's evaluation. Tumor imaging with CT or magnetic resonance imaging (MRI) will be done at the end of first and second treatment cycles, then every two treatment cycles thereafter. The efficacy will be assessed per RECIST version 1.1 by investigators. Safety assessment including vital signs, physical examination, blood and urine analysis, liver, kidney and thyroid function tests, electrolyte profile, electrocardiogram and ECOG performance status will be done every two weeks for one-two cycles, and at the end of each subsequent cycle. Adverse events will be graded according to the National Cancer Institute Common Terminology Criteria for Adverse Events (version 4.0). Survival status will be followed up every two months until death or loss to follow-up.

In the extension phase, subjects in the Apatinib group will continue the treatment when anticipated to benefit from apatinib treatment. For the subjects in the control group, they will be allowed to receive apatinib upon experiencing radiographic disease progression (PD) per RECSIT v1.1 by investigator. Extended treatments are terminated after progression disease, intolerable toxicity, and withdrawal of informed consents during extension phase.

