## 3.3 Sample Size

Sample size determination is performed by PASS 11 software with group sequential log-rank test settings. Assuming a median PFS of 5.8 months in control group, and a median PFS of 12 months in treatment group; subjects randomly assigned to two group by a ratio of 1:1, with an enrollment time of 24 months and a follow-up of 12 months; 50 subjects in each group, to observe 37 PFS events in the treatment group and 46 PFS events in the control group, will provide 90% power to detect a difference between groups using a log-rank test with a two-sided significance level ( $\alpha$ )=0.05. With a 15% drop-out rate, each group will require 59 people, for a total sample size of 118 subjects.

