# 4.5 Termination Criteria

Termination of the treatment does not mean the withdrawal from the study. Subjects must continue to complete the remaining study visits as required by the protocol. If the subject meets any of the following criteria, the treatment must be terminated:

- 1. Subjects withdraw their informed permission and request to be removed from the study.
- 2. Progressive disease is confirmed by investigator.
- 3. Pregnancy during the study.
- 4. the subjects cannot tolerate the toxicity after dose adjustment.
- 5. Other situations indicating the need to withdraw from the study.

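### Section 7.5 puts survival follow-up under the imaging stop rule, contradicting section 3.1 and leaving the collection of deaths for overall survival open to misreading

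*Protocol*

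**What the plan says.** Four parts of the protocol bear on how long survival is followed.

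- **Section 3.1 (overall design):** "Survival status will be followed up every two months until death or loss to follow-up". Progression, crossover and new treatment do not end it.
- **Section 7.5, entry:** among others, subjects with "progressive disease in the randomization phase or progressive disease in the extension phase can enter the survival follow-up period".
- **Section 7.5, both bullets:** "survival follow-up and imaging efficacy evaluation should be conducted once every 2 months until imaging progression or other anti-tumor treatment is started". The bullets differ only in whether a catch-up evaluation is needed first. The frequency and the stop are the same in both.
- **Section 7.5, last sentence:** "During the follow-up period, the time of death or loss of follow-up and other anti-tumor treatment is recorded".

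The schedule in section 7.1 has a row for time of death. It is marked only in the last column, which appears to be the two-monthly follow-up column (the table layout is damaged in the text at hand). Section 4.5 adds that "Termination of the treatment does not mean the withdrawal from the study" and that the remaining protocol visits still have to be completed.

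The data are needed because section 2.2 lists, as a secondary objective, "To assess the overall survival (OS) in subjects treated with apatinib, compared with placebo". Section 10.2.1 provides for Kaplan-Meier estimates of OS and a log-rank comparison between groups.

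**The concern.** Imaging and survival contact serve different endpoints and normally end at different times. Scans may reasonably stop once progression is documented. Survival contact has to run until death, loss to follow-up or study closure. Section 7.5 joins the two in one sentence with one stop, and that stop is right for neither section 3.1 nor the OS objective.

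Section 7.5 is the section that tells sites what to do at follow-up visits, so a coordinator may well work from it rather than from the design summary. If survival contact ended at the stop in 7.5, OS would be censored at a point tied to progression or to a change of therapy. Both are related to prognosis, whereas Kaplan-Meier and log-rank methods assume that censoring is not. Deaths that nobody asked about at the time can be hard to recover later.

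**Working it through.** The point is decided by comparing passages. The arithmetic only gives a sense of scale.

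**1. Section 3.1 against section 7.5.** Both set a two-monthly interval for survival follow-up. The end points are death or loss to follow-up in 3.1, and imaging progression or other anti-tumor treatment in 7.5. For anyone who progresses or changes therapy while alive, both cannot be followed.

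**2. Section 7.5 against itself.** Take a subject who enters follow-up because of progression. The stop is imaging progression, which has already happened, so the bullets give this subject no survival visit. If the stop is instead read as a further progression seen during follow-up, contact would still end before death in most such cases. Yet 7.5 calls this the survival follow-up period and names progressed subjects as entrants.

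**3. Do other passages settle it?**

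- The last sentence of 7.5 requires time of death to be recorded during the follow-up period. The only duration that 7.5 gives for that period is the stop in the bullets.
- The schedule row shows that time of death is collected, but not until when.
- Section 4.5 requires the remaining visits under the protocol, which leads back to 7.5.

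These passages point to the intent of section 3.1. None of them states a duration that overrides the bullets.

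**4. The plan's own figures.** The protocol gives no event target or power for OS. The nearest count is for PFS, in section 3.3: "Assuming a median PFS of 5.8 months in control group, and a median PFS of 12 months in treatment group", "with an enrollment time of 24 months and a follow-up of 12 months", with 37 and 46 events among 50 subjects per group. Assuming exponential PFS and uniform accrual, with L = ln 2 / median:

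P(event) = 1 − [exp(−12L) − exp(−36L)] / (24L)

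- Median 12 months: 1 − (0.500 − 0.125)/1.386 = 0.729, and × 50 = 36.5 (stated 37).
- Median 5.8 months: 1 − (0.238 − 0.014)/2.868 = 0.922, and × 50 = 46.1 (stated 46).

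The PFS design reproduces. These figures are not a measure of lost survival follow-up, for the reasons given under the objection.

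**5. Illustration of the OS data at stake.** Section 1.1 puts average survival at 3 to 5 years. Assume exponential OS with a mean m of 36 to 60 months in both groups, 118 subjects, uniform accrual over 24 months and no loss to follow-up. With F the further follow-up after accrual closes:

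Deaths = 118 × {1 − [exp(−F/m) − exp(−(24+F)/m)] / (24/m)}

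| Months since first enrolment | m = 36 | m = 60 |
|---|---|---|
| 36 (F = 12, section 3.3) | 118 × 0.477 = 56 | 118 × 0.325 = 38 |
| 54 (F = 30; December 2016 to June 2021, section 13) | 118 × 0.683 = 81 | 118 × 0.500 = 59 |

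These are the deaths that the rule in 3.1 would aim to capture under these assumptions. How many a literal reading of 7.5 would miss depends on how many progressed subjects enter the extension phase, how long they stay in it, and how many PFS events are deaths. The protocol gives none of these.

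**The case against.** The strongest reply is that no careful reader would stop collecting deaths. Section 3.1 is unambiguous. Section 7.5 itself asks for time of death. It also asks for other anti-tumor treatment to be recorded during follow-up, which suggests that contact goes on after such treatment starts. A survival period that is empty for progressed subjects makes no sense, so the coherent reading is that the stop was meant for imaging. This stands as the likely intent. It does not remove the contradiction, because the bullets name survival follow-up explicitly, twice.

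Two stronger conclusions are tempting.

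- **A reader might infer that OS would be cut off before almost any death,** because some 92% of control and 73% of apatinib subjects are expected to have a PFS event. The protocol does not support this. First progression does not necessarily lead to section 7.5: under sections 3.1 and 7.4, placebo subjects may cross to apatinib and apatinib subjects may continue open-label, with visits every two cycles. Those who enter the extension stay under contact until they leave it. PFS events conventionally include deaths, which are not lost. And the passages that provide for recording death cannot be set aside.
- **A reader might infer that ending scans at new therapy makes PFS censoring informative.** No passage says that PFS is censored at that point. The censoring rule may lie in a statistical analysis plan that is not shown, and scanning beyond a change of therapy is a debated choice that adds procedures.

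It is also fair to say that OS carries no power claim here, and that the permitted crossover limits the OS comparison in any case.

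**Conclusion.** The contradiction is real. As worded, both bullets of section 7.5 end survival follow-up at imaging progression or other anti-tumor treatment. This conflicts with section 3.1 and defeats 7.5's own entry rule. The consequence is a risk and not a certainty: a site working from the bullets could end survival contact at or soon after progression, or when a subject leaves the extension phase, and deaths would then be missing from a secondary endpoint.

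The size of the loss cannot be derived from the protocol. The 38 to 56 deaths at 36 months show only what OS would rest on, assuming exponential survival with the 3-to-5-year mean of section 1.1 in both groups. The primary endpoint and the sample size are untouched. This should be fixed because the repair is nearly free and the data may not be recoverable, but it does not undermine the trial's main comparison.

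**What to change.** Reword both bullets of section 7.5 as two separate rules.

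- **Imaging:** keep the two-monthly evaluation and its present stop, and state that the stop applies to imaging only.
- **Survival:** state that survival status is collected every 2 months until death or loss to follow-up, as in section 3.1, regardless of progression, crossover or new therapy. Let the last sentence of 7.5 and the time-of-death row in section 7.1 refer to this same duration.

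The cost is a wording amendment and a note to sites. It adds no scan and no contact beyond those section 3.1 already requires. If sites have already worked from 7.5, they should be asked to update survival status for subjects whose contact ended at progression or at a change of therapy.

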#### 7.6 Follow-up of AEs

Follow-up and final evaluation should be made for the AEs that have not recovered when the drug is stopped. All subjects should be followed up for 30 days after the last medication to detect any new AE.

# 8 Efficacy evaluation and analysis

The efficacy assessment will be conducted at the end of the first and second cycles, as well as every eight weeks after that. The assessment will take place within 3 days after the completion of each period. From the third cycle, CT or MRI examinations will be performed within 7 days after completing of every two cycles.

Subjects who develop progressive disease during randomization phase will be unblinded and treat with apatinib until disease progression or at the discretion of the investigators.

# 9 Safety Evaluation

# 9.1 AEs

AEs refer to any adverse medical events occurred in the subjects of clinical trials, which may not be related to the treatment. Therefore, AEs can be any sign, symptom, or temporary drug-related disease, which should be considered whether it is related to medication

According to management needs, safety monitoring (reporting AEs or serious AEs) should be carried out from the beginning of subjects' enrollment to the end of the study. AEs occurred after signing the informed consent form and during the treatment are also considered as AEs.

# 9.2 Treatment-related Adverse Events (TRAEs)

TRAEs are defined as all harmful and unexpected medication responses associated with any dose. The drug's reaction implies that there is at least a plausible probability of a causal association between the drug and the AEs, i.e., the relationship cannot be ruled out.

# 9.3 Serious Adverse Events (SAEs)

SAEs refer to the medical events that need hospitalization, extended hospital stays, and is lifethreatening or cause disability, teratogenesis and death during the clinical trials.

#### 9.3.1 Events that should be dealt with as SAEs

In principle, pregnancy and lactation cannot be included. If pregnancy occurs during the trial, the patient should withdraw from the trial immediately and be followed up closely. Even if the mother and child are completely normal without any AEs, the situation should be recorded. Even if the pregnancy does not belong to SAEs, the SAEs report form should be used for reporting.

#### 9.3.2 Events that should not be dealt with as SAEs

Hospitalization due to progressive disease or unexpected reasons such as medical insurance reimbursement does not belong to SAEs. In this study, due to the severity of the disease, some socalled SAEs cases may need to be excluded from immediate reporting:

- A. Hospitalization and surgical treatment are optional
- B. Hospitalization can be chosen to simplify treatment or research measures

# 9.4 Recording and evaluation of AEs

AEs should be described in medical terms. All AEs should be recorded in the corresponding part of the CRF. If it is a SAE, the SAE report form (including initial, follow-up and summary reports) should be completed. All the cases involved in the trial should be included in the summary. The reasons for the cases dropped out or eliminated during the summary should be explained. In case of death or serious toxic reaction in the trial, a detailed case report should be made. The cause of death should be found out and the relationship between the drug and the death should be emphasized. All AEs during follow-up should be closely followed up until they are properly resolved or stable.

The following aspects of each event should be recorded in CRF:

(1) Occurrence time (start time), recovery time (end time).

(2) The researchers are responsible to evaluate and grade AEs, according to the definition of NCI-CTC AE version 4.0.

(3) The possible association between AEs and the drug is evaluated according to the five-grade classification of "definitely related, likely to be related, possibly related, possibly unrelated and irrelevant". The first three levels are judged to be related to the drug. The sum of the three is taken as the numerator in the calculation of the incidence of AEs, and the number of all subjects used to evaluate the safety is taken as the denominator.

Criteria	definitely	likely to be	possibly	possibly	irrelevant
	related	related	related	unrelated	
Reasonable time sequence	Yes	Yes	Yes	Yes	No
Response types of known drugs	Yes	Yes	Yes	No	No
Improved after removing the cause	Yes	Yes	Yes or No	Yes or No	No
Repeated after administration again	Yes	No	No	No	No
There may be another explanation for the response	No	No	No	Yes	No

Table 3 Criteria for determining the relationship between AEs and drugs

(4) Measures taken for the drug (such as continued medication, reduced dosage, continued medication after suspension, withdrawal and other situations, please specify in detail).

(5) Consequences are defined as follows: disappearance, improvement, no improvement, and aggravation

Note: if the patient has the same AE for several times, it must be recorded and reevaluated each time.

